The proposed study is a multi-site 36-week double-blind, placebo-controlled randomized trial followed by an 18-week open label extension with all patients receiving the GLP1RA treatment. Therefore, each subject will be treated for a total of 54 wk. Subjects will be required to travel to one of three research sites (Seattle, Nashville, St. Paul). A flowchart for scheduled study visits (SVs) is outlined below. Before study start, there will be an investigator kickoff and training meeting guided by [name] from Seattle Children's to coordinate and align all assessments and interventions. In addition, Seattle Children's radiology center will provide standardized protocols to the other two imaging centers for consistent imaging techniques and analyses. During the study and after ending the intervention, there will be bimonthly investigator phone or video conferences.

Time Frame/Duration

The timeline for research activities is four years. This is outlined as: Years 1-3: Enrollment and treatment at 3 study sites. Years 3 and 4: hormonal assays. Year 4: completion of final data analyses.

Each patient will be in the study for 56 weeks, including the screening visit.

Data Requirements

A database will be designed for this study using REDCap (Research Electronic Data Capture) hosted at the Institute of Translational Health Sciences of which Seattle Children's and University of Washington are partners. REDCap is a secure, web-based application designed to support data capture for research studies, providing validated data entry, audit trails, and mechanisms for securely importing and exporting data. It will reside on a secure server with exclusive access by research personnel at all study sites. Access is tailored for specific roles to maintain blinding. Subjects are identified with a study identification number.

Study Measures

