Treatment dosage and duration are based on prescribing information and prior successful clinical trial weight loss results.^{31,110} The placebo-control group is an essential arm in this trial as study measures can change over time without drug intervention and it supports the evaluation of efficacy and safety. The drug and placebo kits will be supplied by AstraZeneca, or the current pharmacologic company responsible for ExQW. Exenatide vials or pens 2.0 mg powder for injection will be supplied. All subjects will have weekly phone calls when not coming for a study visit, to check adherence and any potential

adverse effects. Any evidence for adverse effects will be discussed with the PI of each site and safety clinical visits will be considered.

All study medication will be stored/locked in the investigational pharmacy under appropriate temperature conditions. Dispensing and accountability records will be maintained by appropriate staff members.

Analysis

Analysis plan and sample size calculations by Aim.

The research team includes personnel with statistical and data management expertise for overseeing data collection, storage methods, and the following analyses (see letter of support, [name]). Adherence data collected during the placebo run-in phase will be summarized descriptively. All subjects completing the run-in phase will go on to the randomized treatment phase. The primary analyses will use the intention-to-treat (ITT) approach; i.e., subjects will be analyzed according to their randomized assignment regardless of treatment received. In addition, data of all completers will be analyzed separately as a sensitivity analysis. While every attempt will be made to collect complete data and retain all subjects, all sample size and power calculations account for dropout. Statistical methods have been selected to allow for inclusion of partial data. All testing is two-sided and $\alpha=0.05$. Repeated measures analyses will be conducted using SAS (SAS Institute, Inc., Cary, NC, USA) or R (The R Foundation for

Statistical Computing).

Analysis populations: All eligible subjects randomized will be included in the ITT population. The ITT population will be the primary analysis population for all primary, secondary, and tertiary outcomes. The safety population will be the primary population for all safety analyses, and include all subjects who receive at least one dose of study drug or placebo.

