5. SUBJECTS

Subjects

It is anticipated approximately 16 participants will be treated per year (5-6 per study site) during the first three years of the study. We expect to screen 80 subjects to get 48 subjects enrolled and 38 to complete the study (potential dropout rate of rate of 20%). Subjects will be between the ages of 10-25 y old at time of enrollment (11-27 y at end of intervention), and we expect each patient to complete the 56 week study.

Recruitment

We will recruit patients from the endocrinology clinics at the three sites, and will accept referrals from other endocrine providers. We will be advertising the study to other Pediatric Endocrinologists through a secure message board.

Enrollment

The PI at each site will screen and consent/assent subject or designate other qualified study staff to do so. Qualified participants will start with a 2-week placebo run-in to test adherence to the protocol. Immediately afterwards, subjects will be assigned treatment using a permuted-block randomization (1:1) with varying block sizes constructed by the Children's Core for Biomedical Statistics (CCBS) of Seattle Children's Research Institute (SCRI) stratified by study site, two age groups (10-14y, 15-25y), and gender. This is a double-blind study (participants and investigators both blinded). The study statistician will be blinded as well; a second statistician not involved in the conduct of the study will be responsible for the final preparation of the randomization scheme. Only the independent CCBS statistician and dispensing pharmacy at each site will know assigned study medications. It is anticipated approximately 16 participants will be treated per year (5-6 per study site) during the first three years of the study. We expect to screen 80 subjects to get 48 subjects enrolled and 38 to complete the study (potential dropout rate of rate of 20%). As we would expect many of these participants to be prepubertal as they have hypogonadotropic hypogonadism by virtue of their disease, pubertal status will not be used as an inclusion or exclusion criteria for the study.

Inclusion Criteria

- Age 10-25 years at time of enrollment
- Diagnosis of hypothalamic obesity with age- and sex adjusted BMI $\geq 95\%$ or BMI $\geq 30 \text{ kg/m}^2$ if over 18 y
- History of craniopharyngioma or another tumor located in the hypothalamic area
- Hypothalamic lesion documented by neuroradiology
- ≥ 6 months post-surgical or radiation treatment

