- Weight stable or increasing over 3 months prior to screening visit
- Stable hormone replacement for at least 3 months prior to screening visit

Exclusion Criteria

- Renal impairment (GFR<60 ml/min/1.73m² using the Schwarz formula¹¹⁶)
- History of gastroparesis; pancreatitis or gallstones (unless status post cholecystectomy)
- Family history of multiple endocrine neoplasia type 2 or familial medullary thyroid carcinoma metabolic disorders
- Any insulin-treated diabetes mellitus, poorly controlled type 2 diabetes (HbA1c $\geq 10\%$), or any other chronic serious medical conditions such as CVD, malignancy or hematologic disorder, complicated syndromic disorder, or psychiatric disorders (schizophrenia, major depression, history of suicide attempts)
- Calcitonin $>50 \text{ mg/L}$ at screening
- Initiation of weight loss medications within 3 months of screening visit
- Previous donation of blood $>10\%$ of estimated blood volume within 3 months prior study
- Current warfarin use
- Current use of any other GLP1RA
- Untreated thyroid disorder or adrenal insufficiency

- History of bariatric surgery or planned bariatric surgery until end of study
- Pregnancy, lactation or expectation to conceive during study period
- Subject unlikely to adhere to study procedures in opinion of investigator
- Subject with contraindication to neuroimaging by MRI

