6. STUDY PROCEDURES

For the placebo-controlled portion of the trial, each subject will have a screening visit and 4 study visits (weeks 0 [baseline], 6, 18, 36 [end of randomized trial]). Week 36 will also mark the beginning of the open label extension phase which will continue until week 54.

Screening Visit: The study will be explained to patients and their families and written consent/assent will be obtained. Medical history and concomitant medications will be documented. Vital signs will be recorded, including blood pressure, heart rate, respiratory rate and temperature. Body weight (lightly clothed) and height will be measured with a calibrated electronic scale and calibrated stadiometer. Hip and waist circumference measurements will be completed. A physical exam including Tanner staging will be done. This visit will also include:

- Blood draw for safety labs (electrolytes, CBC, lipase, amylase, glucose, transaminases (ALT, AST), creatinine, hemoglobin A1c, and thyroid hormones [TSH and free T4, or in patients with panhypopituitarism, free T4 only])
 - Blood for carcinoembryonic antigen (CEA) and calcitonin samples
- Blood for DNA extraction will be obtained for genetic markers (only at select sites)
- Urine pregnancy testing (HCG) will be done
- Instructions for 24h dietary recall.

Sexually active female participants are required to use birth control, unless they have documented gonadotropin deficiency.

Parents and participants (if appropriate) will be taught how to mix and inject the study medication. Parents/participants should perform a return demonstration before mixing the actual study medication. All teaching will be documented. Prior to leaving the clinic, parents/participants will inject the first dose of study medication under supervision. Dosing will be documented on the dosing log. Participants will be dispensed 1 more vial of study medication (placebo) to be administered at home the following week. The dose will be identical to the dosing provided in the blinded portion of the trial.

[figure not shown]

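### Does the safety population need rewording because it names no randomisation condition and no analysis period?

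*Combined protocol and SAP*

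**What the plan says.** Section 4, under Analysis populations, defines two sets. For efficacy: "All eligible subjects randomized will be included in the ITT population". The safety set is the "primary population for all safety analyses, and include all subjects who receive at least one dose of study drug or placebo". Only the first carries a randomisation condition. The document states no period for counting adverse events (AEs) and no rule for placing a subject in an arm for safety.

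Three dosing phases surround these definitions.

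- **Run-in.** Section 5, Enrollment: "Qualified participants will start with a 2-week placebo run-in to test adherence to the protocol". Randomisation, 1:1, comes directly after it. Section 6, Screening Visit, has the first injection given under supervision at that visit and a second vial sent home for the next week. Section 4, Analysis, adds: "All subjects completing the run-in phase will go on to the randomized treatment phase".
- **Randomised phase.** Weeks 0 to 36, ExQW or placebo.
- **Extension.** Section 4, Study Design, has the randomised phase "followed by an 18-week open label extension with all patients receiving the GLP1RA treatment".

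Section 7 refers AE monitoring, grading and management, and the reports to the data monitoring committee, to a separate Data and Safety Monitoring Plan, which is not among the documents reviewed.

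**The concern.** In a plain parallel-group trial, having had one dose tells you the subject's arm. Here it does not, because nearly everyone receives both products.

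Two problems seem to follow. First, someone who injects run-in placebo and is never randomised meets the safety definition but has no arm. This could happen: the run-in is there to test adherence, and the first injection is given at the visit where creatinine, HbA1c and calcitonin are drawn (Section 6 lists "Blood for carcinoembryonic antigen (CEA) and calcitonin samples"). These results bear on the renal, diabetes and calcitonin exclusions in Section 5, and the text does not say whether they are awaited. Second, AEs from the run-in, the randomised phase and the extension all fall in one undivided set.

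At stake is the between-arm safety reading. Section 4 gives the evaluation of safety as one reason for having a placebo arm. Section 7 places gastrointestinal AEs mainly in the first 6 to 8 weeks on drug. For the placebo arm those weeks begin at week 36, so pooling all follow-up by randomised arm could hide a real drug effect.

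**Working it through.** **1. The plan's own figure is unaffected.** Section 4 claims 85% power with 19 evaluable per group at a standardised effect of 1, two-sided alpha 0.05. The noncentral t calculation has 36 degrees of freedom and noncentrality 1/√(2/19) = 3.08; it gives 85.06%. The safety definition does not enter it.

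**2. Who receives both products.** All 24 ExQW-randomised subjects who take a dose have also had run-in placebo. Placebo-randomised subjects get ExQW if they reach week 36. With the planned 20% dropout balanced by arm, that is 19 to 24 subjects, so 24 + 19 = 43 to 24 + 24 = 48 of 48. Section 5 gives only 38 completers overall. If all 10 losses were in the placebo arm before week 36, the count would be 24 + 14 = 38. Dosing lasts 2 + 36 + 18 = 56 weeks. A placebo-arm completer spends 18/56 = 32% of it on ExQW, and an ExQW-arm completer 2/56 = 3.6% on placebo. Any run-in plus open-label extension produces figures of this kind.

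**3. Never-randomised subjects counted as placebo.** Their number is not given; 80 screened less 48 enrolled = 32 is only a ceiling. Assume AE counts of 8/24 on ExQW (33.3%) and 6/24 on placebo.

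| Extra subjects in placebo column | Placebo rate | Difference (points) | Shift |
|---|---|---|---|
| none | 6/24 = 25.0% | 8.3 | – |
| 2, no events | 6/26 = 23.1% | 10.3 | +1.9 |
| 4, no events | 6/28 = 21.4% | 11.9 | +3.6 |
| 4, one event | 7/28 = 25.0% | 8.3 | 0 |

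**4. Extension events counted by randomised arm.** Take nausea in weeks 0 to 36 as 6/24 on ExQW (25%, the non-diabetic figure in Section 7) and an assumed 2/24 on placebo: a difference of 16.7 points. Suppose 19 placebo subjects switch, 17 of them without earlier nausea (so both earlier cases are among the 19), and the ExQW arm has no new nausea after week 36.

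- New nausea in 0%: placebo stays at 2/24; difference 16.7.
- In 10%: 17 × 0.10 = 1.7, about 2; placebo 4/24; difference 8.3.
- In 25%: 17 × 0.25 = 4.25, about 4; placebo 6/24; difference 0.

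A general form, for complete follow-up and independence between phases, uses p1 for the ExQW rate and p0 for the placebo rate. Over weeks 0 to 36 the difference is p1 − p0. Over weeks 0 to 54 by randomised arm it is p1 − [1 − (1 − p0)(1 − p1)] = −p0(1 − p1). With p1 = 25% and p0 from 0 to 10%, a difference of 25 to 15 points becomes 0 to −7.5.

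**5. What has to happen first.** Step 3 needs an analyst to put people with no allocation into the placebo column. Step 4 needs an analyst to charge placebo with events that occurred on known, open-label ExQW. The documents direct neither, and they specify no drug-placebo AE table. Restricting the comparison to randomised subjects over weeks 0 to 36 removes both effects.

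**6. Do run-in doses count at all?** Section 6, Screening Visit, calls the run-in vial study medication, which suggests yes. Section 7, Potential Risks, item 10, describes the weekly injections of placebo or ExQW as starting at week 0, which suggests the safety definition may mean the two randomised treatments only. The wording is ambiguous, not plainly over-inclusive.

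**The case for a change.** The best case for a change is that the plan shows it can separate phases and does so only for efficacy. The BMI model in Section 4 is piecewise, dividing the randomised phase from what follows, and run-in reporting covers adherence only. Section 7 uses the term treatment-emergent without defining it. Rewording would cost no data, visits or subjects, and settling the rule before unblinding is better than settling it afterwards.

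Most of this stands as description. The text is silent, and a sentence on phases would be tidy. It does not show that an analysis will go wrong. A population definition says who is included; the period counted belongs to the analysis, so the missing window is an absent detail and not an error in the definition. Nor does the silence lose information. AEs are sought at weekly contacts and at visits, and both phase boundaries are fixed study events, so events can be assigned to phases at analysis.

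A related worry is that the committee's semi-annual report comes from a blinded statistician, goes to the study team as well, and has no by-arm version described. That depends on the monitoring plan, which was not supplied and may provide one. Nothing can be concluded from silence here.

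**Conclusion.** The omission is real but is a gap that analysts fill sensibly: summarise randomised, dosed subjects over weeks 0 to 36 by treatment received, and list run-in and open-label events apart. Nothing in the plan stands in the way, so no change is called for.

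The sizes above are illustrations. Apart from the 25% nausea figure, which comes from another study, the event rates are assumed. The number of run-in-only subjects is unknown, and the switcher count assumes dropout balanced by arm. Under those assumptions the mishandling effects range from nil to 3.6 points for run-in dilution, and from nil to loss or reversal of the nausea difference for pooled extension events. Under the ordinary handling both are zero. Power, sample size and the ITT efficacy analysis do not move.

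The conclusion would change if a reporting document called for AE rates by randomised arm over the whole 54 weeks, or placed never-randomised subjects in the placebo column. The documents reviewed do neither.

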Table 1. Summary of Study Measures and Outcomes and Their Use in the Proposed Research

Measure	Domain	Instrument	Aim	Role/Application
$\Delta\text{BMI}\%$	Adiposity	Anthropometry	1	Primary outcome
Total body fat mass	Body composition	DEXA	1	Secondary outcome
Fat and total calorie intake	Post test meal satiety assessment	Free buffet meal analysis	1	Secondary outcome
Glucose tolerance	Glucose tolerance, MetS	Glucose at 0', 120' (OGTT)	2	Secondary outcome
HDL, triglycerides	MetS	Fasting lipids	2	Secondary outcome
hsCRP	Inflammation	hsCRP at fasting time point	2	Secondary outcome
Free living EE	Energy homeostasis	Doubly labeled water	3	Tertiary outcome
Energy intake	Energy intake	24h dietary recall (ASA24)	3	Tertiary outcome
Leptin, adiponectin, sOB-R, α -MSH, HOMA-IR, WBISI	Energy homeostasis, leptin sensitivity, and insulin resistance	Baseline and stimulated hormones	3	Tertiary outcomes and predictors

Aim 1: To test effects of GLP1RA on hypothalamic obesity prospectively.

Sample: Available anthropometry measures will be included in the analyses (see also Fig. 1 below).

Primary outcome analysis: For efficacy analysis the primary outcome is % change in BMI from week 0 (baseline) to 36 wk. A piecewise (separating the randomized and run out phases) linear mixed-effects model¹¹¹ will be fit with % change in BMI from baseline to 36 wk as the outcome; treatment, time, and the interaction between treatment and time as factors of interest; and randomization stratification variables (site, age, and gender) included as covariates. This model is a generalization of analysis of covariance (ANCOVA) that allows all follow-up repeated measures to be included.

Table 2. Additional Descriptive Parameters, Predictors and Covariates used in Study

Measure	Domain	Instrument	Aim
ΔBMI , ΔBMI z-score	Adiposity	Anthropometry	1
Subjective appetite	Hunger and fullness rating	Visual analog scale	1
Syst. & diast. BP	CVD risk factor, MetS	Ambulatory BP	2
Exercise	Physical activity measure	Actigraphy ^{112,113}	3
Energy intake	Energy intake	24h dietary recall	3
Eating behavior	Assessment of overeating and food reward	Overeating (CEBQ), ⁷⁶ & hyperphagia. ⁷⁷	3
Brain lesion score, hypothalamic region and residual lesion volumes	Structural lesion in the pituitary-hypothalamic area	Brain MRI images	3

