Aim 2: To determine effects of GLP1RA on cardiometabolic risk factors. Secondary outcomes analysis: Secondary outcomes are change in the following metabolic CVD risk factors: blood glucose, triglycerides, HDL cholesterol, and hsCRP. All continuous secondary efficacy endpoints will be analyzed using similar repeated measures analyses to those previously described for the primary outcome to examine differences in the change in secondary outcomes, one at time, from baseline to 36 wk. Histograms will be examined, and if data are markedly skewed right, log transformations will be applied prior to analysis. Measures of insulin resistance and insulin secretion will be compared from baseline to 18 and 36 wk to test whether treatment effects are beneficial during the second half of intervention. Sample size and power: Table 3 shows observed relative effect sizes in our preliminary study for between treatment comparison of change from baseline to 3 mo (dataset from previous study²²). Assuming a normal distribution of changes, a type I error rate of 0.05, and dropout rate of up to 20%, a sample size of 24 subjects per group (19 evaluable) will provide 85% power to detect relative treatment effect sizes of 1 or greater (in absolute value) for changes in cardiometabolic risk factors in patients with HO, which is consistent with the preliminary study.

Expected results and benchmarks for success (secondary efficacy endpoints): We expect that GLP1RA treatment will lead to improved metabolic CVD risk factors (higher HDL; lower blood pressure, blood glucose, hsCRP, and triglycerides).

Aim 3: To explore additional outcome measures, and predictors of treatment responses.

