3a: Test GLP1RA treatment on energy homeostasis. Sample: All available EE and energy intake measures from DLW analyses and ASA24 dietary recalls at 0 and 36 wk will be included in the analyses (see Fig. 1). Tertiary outcomes analysis: The tertiary outcomes are change in EE and energy intake from baseline to 36 wk. Separate analyses will be conducted for EE and energy intake. For example for EE, an ANCOVA will be used to model the outcome of change in EE from baseline to 36 wk post-treatment with treatment as the factor of interest and Δ BMI and Δ energy intake included as covariates as both might affect EE independently of drug. A similar ANCOVA will be used to model the outcome of change in energy intake from baseline to 36 wk. Exploratory analyses will examine the change of energy intake after 6 and 18 wk of treatment to estimate effect sizes and inform the design of future studies.

Sample size and power: Assuming a normal distribution of differences, a type I error of 0.05, and a dropout rate of up to 20%, a final evaluable sample size of 19 subjects per group will provide 85% power to detect relative changes (average change divided by the pooled standard deviation (SD) of the change) in EE in relation to energy intake or energy intake in relation to EE of approximately 1 between the two groups. Based on preliminary pooled data from Ambler¹¹⁴ and Eliakim¹¹⁵ et al., the observed

pooled SDs of EE per DLW measures were 162 kcal/d and 155 kcal/d, respectively. Assuming a moderate correlation between baseline and follow-up measures ($r=0.5$), this would correspond to detectable differences of one pooled SD, or 162 kcal/d and 155 kcal/d, respectively. Expected results and benchmarks for success (exploratory efficacy endpoints): We expect that GLP1RA will lead to increased EE adjusted for Δ BMI and Δ energy intake.

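### The Aim 1 model, reused for the change in every continuous secondary outcome, does not list the outcome's own week-0 value as a covariate, so precision is probably lost on moderately correlated secondary outcomes

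*Combined protocol and SAP*

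**What the plan says.** The primary model is in section 4, Analysis, Aim 1 (Primary outcome analysis). It is a piecewise linear mixed-effects model with percent change in BMI as the outcome and treatment, time and treatment by time as the factors of interest. Its covariates are "randomization stratification variables (site, age, and gender) included as covariates. This model is a generalization of analysis of covariance (ANCOVA". That covariate statement is complete as it stands and does not name the week-0 value.

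Aim 2 (Secondary outcomes analysis) carries the approach over, using "similar repeated measures analyses to those previously described for the primary outcome to examine differences in the change in secondary outcomes". Table 1 lists the secondary outcomes as fat mass by DEXA, fat and calorie intake at the buffet, glucose at 0 and 120 minutes, HDL, triglycerides and hsCRP. The visit list in section 6 has all of them measured at study visit 1 (week 0).

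Two other adjustments appear under Study Measures. DEXA is adjusted for height, age, sex and race, and changes in glucose metabolism are adjusted for change in BMI. Neither is the outcome's own baseline.

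Power for Aim 2 is stated on the change scale: "19 evaluable) will provide 85% power to detect relative treatment effect sizes of 1 or greater (in absolute value) for changes in cardiometabolic risk factors". The only baseline to follow-up correlation in the document is in Aim 3a, for energy expenditure: "Assuming a moderate correlation between baseline and follow-up measures", with r = 0.5.

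**The concern.** Analysing change without the baseline as a covariate fixes the slope of follow-up on baseline at 1. When the true slope is below 1, as it is for an only moderately correlated measure with similar spread at both times, regression to the mean stays in the residual and widens the confidence interval. A chance difference between arms at week 0 also carries into the estimated contrast in that particular trial.

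Randomisation is stratified by site, age group and gender only. Nothing in the design balances hsCRP, triglycerides, 120-minute glucose, fat mass or buffet intake between arms, and about 38 completers are expected. The secondary comparisons may therefore be less precise than the data already being collected allow. Leaving baseline handling unstated also leaves a choice between adjusted and unadjusted results open after the data are seen.

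**Working it through.** **Inputs from the plan.** Two-sided alpha of 0.05 (Analysis); "dropout rate of up to 20%, a sample size of 24 subjects per group (19 evaluable" (Aim 2, Sample size and power); 1:1 allocation (section 5, Enrollment); standardised effect of 1, expressed in SDs of change as in Table 3 (for example -4.29/3.84 = -1.12); normally distributed changes.

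**Assumed.** The correlation r between baseline and follow-up for each secondary outcome, and the ratio k of follow-up SD to baseline SD. The plan gives neither.

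**1. The plan's own figure.** Two-sample t test, n = 19 per arm, d = 1, 36 df, noncentrality 1 × √(19/2) = 3.08: power is 85.1%. The normal approximation gives 86.9%. The stated 85% is reproduced. Dropout: 19/0.8 = 23.75, so 24 per arm.

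**2. Effect of baseline adjustment, equal variances (k = 1).** With outcome SD σ at both times:

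- variance of change = 2σ²(1 − r)
- residual variance after baseline adjustment = σ²(1 − r²)
- ratio = (1 + r)/2, so the effective d is 1/√((1 + r)/2), tested on 35 df

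| r | Variance ratio | Effective d | Power | Gain (points) |
|---|---|---|---|---|
| 0.3 | 0.65 | 1.240 | 96.1% | 11.0 |
| 0.5 | 0.75 | 1.155 | 93.3% | 8.3 |
| 0.6 | 0.80 | 1.118 | 91.8% | 6.7 |
| 0.7 | 0.85 | 1.085 | 90.2% | 5.1 |
| 0.8 | 0.90 | 1.054 | 88.5% | 3.4 |
| 0.9 | 0.95 | 1.026 | 86.8% | 1.7 |

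An allowance for the cost of estimating the slope under chance baseline imbalance trims the gain to 7.6 points at r = 0.5 and 4.3 at r = 0.7. A simulation with site, age and gender in both models (8,000 runs per r) gave 80.7% to 89.2% at r = 0.5 (+8.4) and 80.1% to 85.0% at r = 0.7 (+4.9). The levels are lower because of the extra covariates; the gains agree.

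**3. Unequal variances.** In general the ratio is k²(1 − r²)/(1 + k² − 2rk).

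- k = 1.25: ratio 1.1719/1.3125 = 0.893 at r = 0.5, 0.941 at r = 0.6 and 0.981 at r = 0.7. Gains are about 3.6, 2.0 and 0.6 points. At r = 0.8 the true slope rk equals 1 and the gain is nil.
- k = 0.8: ratio 0.48/0.84 = 0.571 at r = 0.5, 0.602 at r = 0.6 and 0.628 at r = 0.7. Gains are about 12.7, 12.1 and 11.5 points.

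**4. Primary outcome.** Table 3 gives an SD of 1.25 for absolute BMI change. With equal variances, r = 1 − 1.25²/(2·SD²). For an assumed baseline BMI SD of 4, 5 or 8 this is 0.951, 0.969 or 0.988, and the gain is 0.8, 0.5 or 0.2 points. Put differently, if baseline BMI has correlation c with percent change, the variance ratio is 1 − c². The gain is 0.3, 1.3, 3.1 and 5.4 points at c = 0.1, 0.2, 0.3 and 0.4, so it passes 5 points only at about c = 0.4.

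**The case against.** The strongest reply is that baseline adjustment was intended. The plan calls the model a generalisation of ANCOVA that takes in all follow-up measures, which can be read as follow-ups for the response and baseline for the covariate. Aim 2 says only that the analyses will be similar. Some Aim 1 text also appears lost in extraction: the description breaks at Table 2 and resumes mid-sentence, and Aim 3b refers back to a within-subject correlation matrix that the visible Aim 1 text does not contain. It cannot be ruled out that baseline handling was stated there. Against this, the covariate statement itself is intact, and the plan's one fully written ANCOVA (Aim 3a, change in energy expenditure) lists treatment, change in BMI and change in energy intake but no baseline energy expenditure. In this document the word ANCOVA does not by itself supply the baseline. What stands is that the plan should say so explicitly.

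A second reply is that no single figure for the loss is supported. That is right. The only r in the plan belongs to a tertiary outcome, fat mass may track its baseline closely, and the gain moves with the variance ratio. The simple ratio also does not describe exactly the models that carry the DEXA or change-in-BMI adjustments.

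A reader might further infer that the secondary estimates are biased or that the 85% is wrong. The documents support neither. Under randomisation the change-score contrast is unbiased on average, chance imbalance matters only conditionally on the baselines observed, and the 85% reproduces for the analysis described.

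**Conclusion.** The point holds as a matter of precision and clarity. The visible plan analyses change in each continuous secondary outcome without that outcome's week-0 value. At the planning effect of 1 SD of change, with 19 per arm and equal variances, adjusting would lift power from 85% to about 93% (r = 0.5), 90% (r = 0.7) or 87% (r = 0.9). Over follow-up SDs of 1.25 to 0.8 times baseline, the gain runs from about 0 to 13 points. These figures rest on assumed correlations and variance ratios and should be quoted as a range.

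It would be tempting to conclude that the primary analysis is materially weakened. It is not: for percent change in BMI the gain is probably under 1 point on the assumed baseline SDs of 4 to 8. The analysis is valid as planned. The change is worth making because the week-0 data are already collected and recruiting more patients would be far harder.

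**What to change.** State in the Aim 2 analysis, and for the Aim 1 secondary outcomes, that each model includes the outcome's week-0 value as a covariate: glucose, triglycerides, HDL, hsCRP, fat mass and buffet intake. Put the baseline on the log scale where the outcome is logged, and add a baseline-by-visit term for outcomes with more than one follow-up. Add baseline BMI to the primary model for consistency. Keep site, age and gender, the DEXA covariates and the adjustment of glucose-metabolism changes for change in BMI. If baseline adjustment was always intended, the same sentence settles it.

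The cost is one sentence of analysis text and one degree of freedom per model, or a few with baseline-by-visit. No new data are needed and the sample size does not change.
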